#### 4.4 PHASE 2A

Once all patients completed Cycle 1 of the dose escalation phase (Phase 1), the SRC reviewed all available safety, clinical, laboratory, and PK data and recommended continuing with the phase 2 portion of the study. The RP2d of AFM24 in combination with atezolizumab was determined. The MTD was not reached. Enrollment into the expansion cohorts for the selected cancer indications in the expansion phase (Phase 2a) began (see Protocol Section **Error! Reference source not found.**).

A Simon two-stage optimal design will be utilized for Expansion Cohorts 1 and 2. Expansion Cohorts 3 and 4 are exploratory with no hypothesis testing. The expansion phase (Phase 2a) of the study is intended to collect preliminary evidence of efficacy and to further confirm the safety of AFM24 in combination with atezolizumab.

During the expansion phase (Phase 2a), up to 130 patients will receive weekly infusions of AFM24 at the RP2D in combination with an every two-week infusion of atezolizumab in four-week cycles in four expansion phase cohorts based on tumor types.

Based on results from dose-escalation phase (Phase 1), additional treatment schedules of AFM24 administration (i.e., q2w) may be explored as part of the expansion phase (Phase 2a) within or across cohorts.

Patients will receive the investigational treatment (AFM24 + atezolizumab) until disease progression, intolerable toxicity, at the investigator's discretion, or patient withdrawal of consent.

#### 4.5 REPLACEMENT OF PATIENTS

In Phase 1 (dose escalation), a patient who did not fulfill the Dose Limiting Toxicity (DLT) requirements (refer to the protocol section **Error! Reference source not found.**) and who discontinued study participation prior to completing the DLT observation period due to any reason other than a DLT, would be replaced for DLT evaluation but will remain in the Safety Analysis Set (see Section 7.1 for definition).

For the dose escalation (Phase 1) and expansion phase (Phase 2a), all patients who begin AFM24 treatment (e.g. Day -7) but discontinue prior to receiving any amount of atezolizumab will be replaced but will remain in the overall Safety Analysis Set. A replacement patient will be enrolled and assigned the same cohort or dose level.

#### 4.6 STUDY TREATMENT

AFM24 will be administered as an i.v. infusion, gw (or g2w as part of the Phase 2a in case

Review Status: Draft Version: 2.0 Version Date: 22-JUL-2024

additional treatment schedules of AFM24 administration are explored), in 4-week cycles. Atezolizumab will be administered as i.v. infusion, q2w, in 4-week cycles. Refer to the Pharmacy Manual for full details regarding study drug administration.

#### 4.6.1 Phase 1 Treatment Assignment and Schedule

For the dose escalation phase (Phase 1), patients received AFM24 and atezolizumab in an open label fashion according to the following treatment schedule for their assigned cohort:

- Cohort 1 (N= 4)
   160 mg AFM24 i.v. qw + Atezolizumab 840 mg i.v. q2w
- Cohort 2 (N= 6)
   480 mg AFM24 i.v. qw + Atezolizumab 840 mg i.v. q2w

#### 4.6.2 Phase 2a Treatment Schedule

Patients who are remain eligible post-evaluation for AFM24-hypersensitivity during the safety-lead in phase (Day -7 through Day -1) will receive the investigational treatment (AFM24 + atezolizumab) as per the following regimens, with the RP2D defined as 480 mg:

- EXP-1 (EGFR-wild type (WT) Non-small cell lung cancer (NSCLC)):
   AFM24 i.v. qw or q2w at RP2D dose + Atezolizumab 840 mg i.v. q2w
- EXP-2 (gastric or gastro-esophageal junction [GEJ] adenocarcinoma): AFM24 i.v. qw or q2w at RP2D dose + Atezolizumab 840 mg i.v. q2w
- EXP-3 (Hepatocellular Carcinoma, Hepatobiliary-, or Pancreatic Adenocarcinoma): RP2D AFM24 i.v. qw or q2w at RP2D dose + Atezolizumab 840 mg i.v. q2w
- EXP-4 (advanced or metastatic NSCLC harboring a targetable EGFR kinase domain mutation): RP2D AFM24 i.v. qw or q2w at RP2D dose + Atezolizumab 840 mg i.v. q2w

Additional treatment schedules of AFM24 administration (e.g., every 2 weeks) may be explored as part of the Phase 2a within or across cohorts.

# 4.7 SAFETY REVIEW COMMITTEE (SRC)

The SRC convened to make a decision on the dose escalation in the Phase 1.

All details regarding the SRC composition, meetings, reviewed data and the decision-making process will be documented in the study-specific SRC Charter.

# 4.8 INDEPENDENT DATA MONITORING COMMITTEE (IDMC)

The IDMC, consisting of clinical experts who are not directly involved in this clinical study, will be established for the Phase 2a of the study. The IDMC will review all safety data generated throughout the dose expansion phase (Phase 2a) of the study on a regular basis. Based on the outcome of their review, the IDMC will provide recommendations to the Sponsor with regard to study conduct or study procedures. The set-up and operational process for this IDMC will be described in a separate IDMC charter.

Review Status: Draft Version: 2.0 Version Date: 22-JUL-2024

#### 5. SAMPLE SIZE AND POWER CALCULATION

Please refer to the protocol section 9.1 for sample size justifications.

#### 6. ANALYSIS ENDPOINTS

Please refer to the protocol section 3 for Objectives and Endpoints.

#### 7. ANALYSIS POPULATIONS

#### 7.1 SAFETY ANALYSIS SET

The Safety Analysis Set will consist of all patients who received at least any amount of AFM24 or atezolizumab. The Safety Analysis Set will be the primary population for all safety related endpoints except determination of the dose-DLT relationship.

# 7.2 FULL ANALYSIS SET (FAS)

The FAS will consist of all patients who received at least any amount of both AFM24 and atezolizumab. The FAS will be the primary population for all efficacy related endpoints.

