### 4. STUDY DESIGN

### 4.1. Overall Study Design

AFM24-102 is a Phase 1/2a open-label, non-randomized, multicenter, dose escalation and expansion study evaluating AFM24 in combination with atezolizumab (investigational treatment: AFM24 + atezolizumab) in patients with select *EGFR*-expressing advanced solid malignancies whose disease has progressed after treatment with previous anticancer therapies.

There will be 2 parts in this study: a dose escalation phase (Phase 1) and an expansion phase (Phase 2a). Patients will qualify to receive the investigational treatment (AFM24 + atezolizumab) in the dose escalation phase (Phase 1) or in the expansion phase (Phase 2a) only if they are deemed eligible post the safety lead-in phase where they will receive a single i.v. AFM24 infusion (see Section 4.2.2). Patients who qualify the safety-lead in phase will receive AFM24 i.v. infusion, qw, in 4-week cycles and atezolizumab i.v. infusion, q2w, in 4-week cycles.

Overall, the study will consist of following periods:

- Pre-Screening period
- Screening period ( $\leq 21$  days prior to Day -7)
- Safety lead-in phase (Day -7 through Day -1) to evaluate patient's hypersensitivity to AFM24 *only* infusion

**Note:** Some of the screening assessments will be allowed during the safety lead-in phase as well. Please review the Inclusion Criteria (Section 5.1) and Exclusion Criteria (Section 5.2) to see allowed time periods of screening assessments.

- Treatment Period (AFM24 + atezolizumab)
  - o Dose Escalation Phase (Phase 1)
  - o Expansion Phase (Phase 2a)

**Note**: Patients will receive the investigational treatment (AFM24 + atezolizumab) until disease progression, intolerable toxicity, Investigator discretion, or patient withdrawal of consent.

- Follow-Up
  - End of Treatment (EOT) Visit (14 days [±2 days] after the last administration of AFM24 or before start of any new anti-cancer treatment whichever is sooner)
  - O Safety Follow-Up Visit (30 days [±5 days] after the last administration of study treatment or before start of any new anti-cancer treatment whichever is sooner)
  - Long-term follow-up (patients will be contacted every 3 months [±2 weeks] to collect data on their subsequent therapies and disease status.

**Note**: Patients who are permanently discontinued from the study during the safety lead-in phase should complete the EOT visit and the Safety follow-up visit but will not be required to complete the long-term follow up.

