# 4.2.2. Safety Lead-In Phase (for Both the Dose Escalation Phase [Phase 1] and the Expansion Phase [Phase 2a])

Seven days prior to Cycle 1 Day 1 (C1D1) (i.e., at Day -7), patients will receive a single dose of AFM24 (dose assigned to a given cohort) and will be observed for any AE for 1 week (from Day -7 through Day -1, the safety lead-in phase). Patients who have any Grade ≥3 cytokine release syndrome (CRS) or IRR symptoms lasting >6 hrs or any other possibly treatment-related Grade ≥3 non-hematological TEAEs or clinically significant hematological Grade ≥3 TEAEs during their

. Patient's eligibility criteria must be re-confirmed on or within 7 days before Day -7, before the administration of the first AFM24 infusion; please refer to inclusion and exclusion criteria sections (Sections 5.1 and 5.2, respectively) to see allowed time periods of screening assessments.

Patients not proceeding to combination therapy (AFM24 + atezolizumab) will be replaced.

Note: Patients are required to receive premedication approximately 1 hour before each dose of AFM24; a list of premedications is provided in Section 6.3.

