## **4.2.3.1.** Definition of Dose-Limiting Toxicity (DLT)

DLT is defined as an AE or abnormal laboratory value assessed as unrelated to underlying disease, disease progression, inter-current illness, or concomitant medications, that occurs ≤28 days following the first dose of AFM24 in combination with atezolizumab (Cycle 1) and that meets any of the following criteria shown in Table 1. Clinically relevant toxicities will be evaluated according to the National Cancer Institute (NCI)/National Institutes of Health (NIH) Common Terminology Criteria for Adverse Events (CTCAE) v5.0. Patients who experience a DLT during Cycle 1 must permanently discontinue AFM24 and atezolizumab.

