## 4.2.5. Follow-Up

Patients who are permanently discontinued from the study during the safety lead-in phase should complete the EOT visit and the safety follow-up visit but will not require the long-term follow-up.

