#### 8.3.2.2. Overall Survival

Overall survival (median) is determined by looking at the time from initial date of treatment to the date of death due to any cause. Survival data will be collected throughout the active treatment phase and during the long-term follow-up phase. Survival follow-up after patient discontinuation of investigational product will be conducted approximately every 12 weeks to assess for survival until patient death or withdrawal of consent.

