## 9.3.2. Efficacy Analyses

Objective Response: The number and percentage of patients achieving each category of response for OR (including CR and PR) will be provided. Results will be presented by percentages and 95% CI.

Clinical benefit rate (defined as CR or PR [any duration] OR SD ≥24 weeks): Results will be presented by percentages and 95% CI.

Disease control rate (DCR) at months 3, 6, 9, 12 and 15, as defined by achieving CR and/or PR and/or SD assessed by RECIST v1.1 will be presented by percentage rates and where appropriate the 95% CIs.

Progression-free survival will be measured from the date of the first dose of AFM24 and atezolizumab study drug to the date of disease progression or death from any cause, whichever occurs first.

Overall survival will be measured from the date of the first dose of AFM24 study drug to the date of death for any cause.

Duration of response will be measured from the date at which response criteria are met for CR or PR until the date of recurrence, PD, or death. Progression-free survival, overall survival, and DOR will be summarized using the Kaplan-Meier method. Censoring rules will be provided in the statistical analysis plan.

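### As the protocol words it, overall survival runs from the Day -7 AFM24 dose but is analysed in a set that patients join only at C1D1, which builds in about 7 death-free days: a small bias, always favourable

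*SAP*

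**What the plan says.** **OS origin.** Protocol 9.3.2 states: "Overall survival will be measured from the date of the first dose of AFM24 study drug to the date of death for any cause". Protocol 8.3.2.2, under efficacy parameters, words it differently: "time from initial date of treatment to the date of death due to any cause".

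**First AFM24 dose.** Protocol 4.2.2 states: "Seven days prior to Cycle 1 Day 1 (C1D1) (i.e., at Day -7), patients will receive a single dose of AFM24". Protocol 4.1 describes this week as "Safety lead-in phase (Day -7 through Day -1) to evaluate patient's hypersensitivity to AFM24", using AFM24 alone. The combination with atezolizumab begins with Cycle 1 (Protocol 4.2.3.1).

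**Population.** SAP 7.2 states: "The FAS will consist of all patients who received at least any amount of both AFM24" and atezolizumab. It adds: "The FAS will be the primary population for all efficacy related endpoints". SAP 8.6.1 runs all efficacy tables on this set, and Protocol 9.1 gives the same definition.

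**Patients who stop in the lead-in.** They are replaced and remain only in the Safety Analysis Set (Protocol 5.6, SAP 4.5). Under Protocol 4.2.5 they "should complete the EOT visit and the safety follow-up visit but will not require the long-term follow-up".

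**PFS origin.** Protocol 8.3.2.3 counts from the initial treatment date. Protocol 9.3.2 counts from the first dose of AFM24 and atezolizumab.

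**The concern.** Time zero for OS precedes the event that decides who is analysed. FAS membership is fixed when atezolizumab is started at C1D1, but the clock has already run for a week. Deaths in that week are removed by definition, while the week itself is credited as survival to every patient who remains. This is immortal time, and it can only favour the treatment.

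The trial has no randomised arm in which the same credit would cancel, so any OS curve will be read against outside figures. No landmark, delayed-entry or sensitivity analysis for this appears in the visible text.

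A second, smaller matter is that the two protocol sections word the OS and PFS origins differently. A programmer could start the two curves on the same day or a week apart.

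**Working it through.** **Inputs**
- OS origin: first AFM24 dose (Protocol 9.3.2), which is Day -7 (Protocol 4.2.2).
- FAS entry: first atezolizumab in addition to AFM24 (SAP 7.2), given at C1D1.
- Phase 2a planned size: 130 (Protocol 4.3; 18 + 130 = 148 reproduces the planned total).
- Median OS: the documents give none. I assume 4, 6, 8 and 12 months, at 30.44 days per month, with a constant hazard.

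**Step 1: length of the interval.** Day -7 through Day -1 is 7 days, and C1D1 follows. On schedule, every FAS survival time contains 7 days in which death was impossible, so the FAS curve stays at 100% for that week. The 7 days are nominal: visit windows are not visible, and a delayed C1D1 lengthens the interval.

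**Step 2: effect on the median.** Moving the origin of the FAS curve to C1D1 takes 7 days (7/30.44 = 0.23 months) off each survival time. Relative to a median m counted from C1D1, the overstatement is 7/m.

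**Step 3: deaths excluded and effect on the curve.** With constant hazard from Day -7, the share dying in the week is q = 1 − exp(−ln 2 × 7/m). Restricting to survivors gives S_FAS(t) = S(t)/(1 − q). Where the true survival of all treated patients is 50%, the FAS curve therefore reads 50%/(1 − q).

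| Assumed median | m (days) | 7/m | q | 130 × q | FAS curve where truth is 50% |
|---|---|---|---|---|---|
| 4 months | 121.8 | 5.7% | 3.9% | 5.1 | 52.0% |
| 6 months | 182.6 | 3.8% | 2.6% | 3.4 | 51.3% |
| 8 months | 243.5 | 2.9% | 2.0% | 2.6 | 51.0% |
| 12 months | 365.2 | 1.9% | 1.3% | 1.7 | 50.7% |

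**Step 4: if the first-week hazard is low.** As q goes to 0, 50%/(1 − q) goes to 50%. If nobody is lost in the lead-in, the FAS and the Safety Analysis Set are the same patients, and OS from the first dose is unbiased. The table is therefore an upper range for the immortal-time component on schedule, not an estimate of what will be seen.

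**Step 5: what a C1D1 origin leaves behind.** Patients removed in the lead-in for toxicity or deterioration are still absent from the FAS. As an illustration, assume 5% are lost with a median OS of 1 month, and the rest have a median of 6 months from C1D1. The medians are then:
- 189.6 days in the FAS from Day -7;
- 182.6 days in the FAS from C1D1;
- 176.6 days in the Safety Analysis Set from Day -7.

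The change of origin removes 7.0 of the 13.0 days; 182.6 − 176.6 = 6.0 days of selection remain. If the lost patients have a median of 3 months instead, the Safety Analysis Set median is 182.8 days and almost nothing remains. This selection is separate from the 7 days.

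**The case against.** **The SAP may already deal with it.** The SAP's own time-to-event text is not visible: the Phase 1 part of 8.6.3 is largely blank and the Phase 2a part of 8.6.2 begins partway through. A C1D1 origin or a sensitivity analysis could be there. This stands, so the point rests on Protocol 9.3.2 alone.

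**Time zero is not settled.** Protocol 8.3.2.2 uses the initial treatment date. The protocol calls the combination the investigational treatment, lists the lead-in apart from the treatment period (4.1), and in 4.2.3 counts the first four treatment weeks from C1D1. On that reading there is no immortal time. Protocol 9.3.2, however, names AFM24 specifically, and the first AFM24 dose is on Day -7. The ambiguity itself needs resolving.

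**It is small and drives no decision.** OS is not among the visible primary or secondary endpoints (Protocol 3), and no visible hypothesis or sample size uses it. With an assumed 30 to 40 patients per cohort, the 95% interval around 50% survival is about ±17.9 to ±15.5 points (1.96 × √(0.25/n)), against a shift of 0.7 to 2.0 points. Patients are ECOG 0 or 1, so few first-week deaths are plausible. All of this stands and limits the weight of the point, but the direction remains fixed and removal is nearly free.

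**Lead-in deaths are reported anyway.** SAP 8.7.2 summarises and lists all deaths. This is true, but they are not tied to the OS result.

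A reader might also infer that the Safety Analysis Set cannot help, because lead-in discontinuations have no long-term follow-up. The documents do not support that. Protocol 4.1 and 4.2.5 still require the end-of-treatment visit and the safety visit about 30 days after the last dose. Deaths in the 7-day window should therefore be known, and these patients can be censored at last contact. Early censoring is a limitation, not a bar.

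**Conclusion.** The point holds as a minor correction. On the wording of Protocol 9.3.2, OS in the FAS carries about 7 nominal death-free days by construction. The effect is at most about 7 days of the median, or 1.9% to 5.7% for assumed medians of 12 to 4 months, and less when the first-week hazard is low. This assumes C1D1 on schedule, a roughly constant hazard for the upper figure, and no different rule in the SAP text that cannot be seen. The response rate is untouched.

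Two stronger readings are tempting but not supported:
- That the median and every landmark rate are inflated by exactly 7 days. The size depends on how many patients are lost in the lead-in, and the documents do not say.
- That PFS and OS certainly start a week apart. Protocol 8.3.2.2 and 8.3.2.3 give them the same origin; only 9.3.2 separates them. What is established is inconsistent wording. If 8.3.2.3 is read as Day -7, PFS, a Phase 2a secondary endpoint, carries the same 7 days.

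**What to change.** 1. In the SAP, state one origin for OS and PFS in the FAS: the date of the first atezolizumab dose (C1D1). Describe the result as survival among patients who started the combination. Align Protocol 8.3.2.2, 8.3.2.3 and 9.3.2 in the amendment that SAP section 10 already announces; until then, list the change in that section.
2. Report, by cohort, the number of deaths and the number of discontinuations between Day -7 and C1D1. This shows the selection that the new origin does not remove.
3. Add a supportive OS curve from Day -7 in the Safety Analysis Set, with lead-in discontinuations censored at last contact and that early censoring stated as a limitation.

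**Cost.** One SAP sentence, a changed start date in the program, one line of counts and one supportive output. All dates are already recorded and no new data are needed. Reported OS becomes about 7 days shorter, and so does PFS if it would otherwise have been counted from Day -7.

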# 7.3 Dose-Determining Set (DDS)

The DDS will consist of all patients in the Safety Analysis Set, who have either (a) experienced DLT at any time during Cycle 1, or (b) met the minimum safety evaluation requirements without experiencing DLT within Cycle 1.

Patients must receive ≥ 75% of their assigned AFM24 dose in Cycle 1, receive ≥ 50% of their assigned atezolizumab dose in Cycle 1, complete the 28-day DLT observation period and have at least one post-baseline assessment of the following safety parameters: Physical Examination, Vital Signs, Laboratory, and Electrocardiogram (ECG), or have had a DLT within the first cycle of treatment to be considered evaluable for DLT.

#### **7.4 PK SET**

The PK set consists of all patients who have received at least 1 adequately documented dose of AFM24 and have at least 1 adequately documented post dose PK measurement.

#### 8. ANALYTICAL PLAN AND STATISTICAL METHODS

#### 8.1 GENERAL CONVENTIONS AND STATISTICAL CONSIDERATIONS

All analyses will be performed using SAS® statistical analysis software (SAS, SAS/GRAPH and SAS/STAT; version 9.4 or higher of SAS for Windows [SAS Institute Inc.; Cary, NC, USA]).

Descriptive statistics for continuous variables will include the number of patients, mean, standard deviation, median, minimum, and maximum values. All raw data will be presented to the original number of decimal places. Means, medians, and confidence intervals will be presented to 1 more decimal place than in the raw data. Standard deviations will be presented to 2 more decimal places than in the raw data. Summary statistics for categorical variables will contain count and percentage. Percentages will be presented to one decimal, except for one hundred percent, which will be presented as 100%. Unless otherwise specified, percentages for baseline summaries will be based on the total number of patients in the treatment arm or

Review Status: Draft Version: 2.0 Version Date: 22-JUL-2024

overall, for the indicated population (dependent on table column heading), percentages for post-baseline summaries will be based on the total number of patients with non-missing values in the treatment arm or overall.

Change from Baseline at Visit X is defined as Test Value at Visit X – Baseline Value.

Unless otherwise stated, all analyses will be descriptive in nature, no formal statistical comparisons of data from different arms or cancer type will be done.

Data will be listed individually by patient.

The tables and the listings will be done separately for two phases. Phase 1 summaries will be presented by the dose level, and Phase 2a summaries by Expansion Cohort.

## 8.2 DEFINITION OF BASELINE, STUDY VISITS, AND VISIT WINDOWS

Baseline is defined as the last non-missing observation prior to the first dose of either AFM24 or atezolizumab (screening assessment for most of the parameters, or Day -7 pre-dose, where applicable).

Data will be analyzed in accordance with the visits recorded in the eCRF. No visit reassignment will be done.

Time points for analysis of vital signs will be assigned using protocol-defined windows (refer to Protocol section 8.2.4 table 3).

